11.8. Testing Strategy

Since this is an exploratory proof of concept study, no formal testing strategy or adjustments of the Type I error will be employed for the evaluation of secondary or exploratory endpoints. Estimates and CIs for treatment groups and from pairwise comparisons will be reported in an exploratory manner.

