3.3. Rationale for Dose Selection

Preliminary safety, tolerability, PK, and PD data from APD791-106 Phase 1 clinical study suggests that IV temanogrel administered at single doses up to 40 mg demonstrated an acceptable safety and tolerability profile in healthy adult humans. When administered over a period of 5 minutes, the 40 mg IV temanogrel dose exhibited a similar maximal exposure (mean C_{max} 1840 ± 349 ng/mL) and lower overall exposure (mean area under the plasma concentration vs. time curve from time zero to the time of the last quantifiable plasma sample [AUC_{0-t}] 732 ± 163 ng/mL/h) compared with the highest single oral dose (320 mg) of temanogrel studied in the absence of DAPT (mean C_{max} 1610 ± 473 ng/mL, AUC_{0-t} 2831 ± 1146 ng/mL/h).

A dose-dependent inhibition of 5-HT-mediated platelet aggregation was observed with near maximal inhibition at doses of 20 mg and greater over 4 hours after dosing. Previously, a near-complete attenuation of 5-HT-mediated vasoconstriction in the presence of ketanserin (a 5-HT_{2A} receptor antagonist with receptor binding affinity and functional activity similar to temanogrel) was observed at a concentration of 200 nM. In the Phase 1 study of single doses of IV temanogrel, all subjects who received the 40 mg IV temanogrel maintained exposure above this concentration during the 1 hour following dosing, which should ensure an appropriate coverage over the duration of a PCI procedure.

Thus, in the current study single 20 and 40 mg doses of IV temanogrel will be administered to evaluate a range of doses across concentrations expected to elicit meaningful PD effects in the setting of PCI. In the IV and oral Phase 1 clinical studies, adverse events, cardiovascular parameters, and laboratory tests were closely monitored across the exposures associated with these doses, and no notable adverse effects occurred.

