11. PLANNED STATISTICAL METHODS

11.1. General Considerations

Details regarding the statistical analyses will be provided in a Statistical Analysis Plan (SAP), which will be finalized prior to study database lock (unblinding).

Continuous variables will be summarized using the number of observations (n), mean, standard deviation (SD), median, minimum, and maximum. Categorical variables will be summarized using frequency counts and percentages.

Unless otherwise specified, continuous endpoints will be analyzed using analysis of covariance (ANCOVA) with a model that includes treatment group and randomization stratification factor as factors and Baseline IMR value and Baseline value as covariates. Least square means, standard errors (SEs), and 95% confidence intervals (CIs) for the treatments and their difference will be presented together with their p-value.

Proportion-based endpoints will be analyzed by either the Cochran-Mantel-Haenszel method adjusting for randomization stratification factor. The number and percentage of subjects achieving the goal and the difference in proportion between treatment groups achieving the goal, along with p-value and the 95% CIs will be reported. The odds ratio relative to placebo and percentage of difference from placebo will be presented together with corresponding 95% CIs and the p-value.

Pairwise comparisons of each temanogrel treatment group compared to placebo will be conducted. In addition, analyses of the pooled temanogrel treatment groups compared to placebo will be conducted.

Where statistical assumptions (eg, normality, proportional odds) are not met, alternative approaches will be evaluated (eg, non-parametric analysis, log transformation).

Efficacy data will be analyzed by randomized treatment, while safety data will be analyzed by actual treatment received.

All secondary and exploratory analyses will be interpreted in an exploratory manner.

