11.2. Determination of Sample Size

This study is planned to randomize, treat, and complete safety, tolerability, PK, and PD assessments in approximately 99 subjects (12 in Stage A, 87 in Stage B).

It is assumed that the primary endpoint, which is the change from Baseline in IMR measured immediately after PCI, is normally distributed with a mean of 6 and SD of 3.5. Assuming a 1:1:1 randomization, 90 evaluable subjects (30 subjects in each of the 2 temanogrel treatment groups and placebo) is sufficient to achieve at least 90% power to detect a treatment effect of 3 (a clinically significant reduction of 50% from placebo) between each of the temanogrel treatment groups and placebo by a 2-sample t-test using a 2-sided significance level of 0.05.

The primary endpoint analysis will be based on pooled data from subjects in Stage A and Stage B.

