11.5. Efficacy Analyses

The primary and secondary endpoints will be analyzed using the Full Analysis Set (FAS). Other important statistical considerations such as sensitivity analyses and subgroup analyses will be described in the SAP.

The primary endpoint of the study is the change from Baseline in IMR measured immediately after PCI. The primary PD analysis will be analyzed using ANCOVA with a model that includes treatment group and randomization stratification factor as factors and Baseline IMR as a covariate. Least square means, standard errors (SEs), and 95% CIs for the treatments and their difference will be presented together with their p-values.

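### Does the plan need to say which primary-endpoint contrast decides, and whether the two dose comparisons are adjusted for multiplicity?

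*Combined protocol and SAP*

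**What the plan says.** Section 11.2 gives the only sizing statement. With 30 evaluable subjects per arm, the trial has at least 90% power for a difference of 3 IMR units "between each of the temanogrel treatment groups and placebo by a 2-sample t-test using a 2-sided significance level of 0.05". No split of the 0.05 is mentioned.

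Section 11.1 plans a comparison of each dose with placebo and then, as an addition, states that "analyses of the pooled temanogrel treatment groups compared to placebo will be conducted". The same section says "All secondary and exploratory analyses will be interpreted in an exploratory manner" and gives no label to the primary analysis.

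Section 11.5 describes the primary ANCOVA, from which "95% CIs for the treatments and their difference will be presented together with their p-values". It attaches no decision rule.

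Section 11.8 opens by describing the whole study as an exploratory proof of concept. It then states that "no formal testing strategy or adjustments of the Type I error will be employed for the evaluation of secondary or exploratory endpoints", and continues: "Estimates and CIs for treatment groups and from pairwise comparisons will be reported in an exploratory manner". The synopsis repeats the last two statements without the opening description.

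Sections 11.1 and 11.5 leave further detail to the SAP. The Note to File of 07 October 2022 records that enrolment was stopped and that the SAP stayed at draft v0.3 and would not be finalized.

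**The concern.** Two features of the text catch the eye. The waiver in section 11.8 covers secondary and exploratory endpoints only, section 11.1 calls only those analyses exploratory, and section 11.2 sizes the primary contrasts like ordinary 0.05 tests. That suggests the primary contrasts are meant as formal tests. Yet the second statement in section 11.8 names no endpoint, and the primary contrasts are pairwise comparisons, so it can be read as making them exploratory as well.

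Three contrasts will also come with p-values, and none is named as the one that decides. Section 3.2 says the results will inform the design and dose selection of later studies. Section 3.3 gives some reason to think the doses may differ: near-maximal platelet inhibition is reported from 20 mg upward, but cover against vasoconstriction is cited only for the higher dose ("all subjects who received the 40 mg IV temanogrel maintained exposure above this concentration during the 1 hour following dosing"). If the contrasts disagreed, a reader could choose among them after seeing the data. If an adjustment had been intended, the 90% power per dose might not hold.

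**Working it through.** **Inputs.** From section 11.2: difference 3, SD 3.5, 30 evaluable per arm, 1:1:1 allocation, "2-sample t-test using a 2-sided significance level of 0.05". From the synopsis: 29 per arm in Stage B, plus 4 per arm from Stage A (4 at 20 mg, 4 at 40 mg and 2 + 2 placebo). That makes 33 per arm if both Stage A doses carry forward and every subject is evaluable. The gain from adjusting for Baseline IMR is ignored because no correlation is given.

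**1. The plan's own figure.** Noncentrality = 3 / (3.5 × √(2/30)) = 3 / 0.904 = 3.32, with 58 degrees of freedom. The noncentral t distribution gives power of 90.4%. The normal approximation gives 91.3%, and a requirement of 2 × (1.960 + 1.282)² × 3.5² / 3² = 28.6, so 29 per arm. The stated figure of at least 90% is right at unadjusted two-sided 0.05.

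**2. Power per dose under other rules, effect 3 in both doses.** The unadjusted and Bonferroni rows use the two-sample noncentral t. The other rows are simulated (400,000 trials, shared placebo arm, three-arm variance), a basis on which unadjusted power is 90.6% and 93.1%.

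| Rule | 30 per arm | 33 per arm |
|---|---|---|
| Unadjusted 0.05 | 90.4% | 92.9% |
| Bonferroni over two doses (0.025) | 84.3% | 87.9% |
| Bonferroni over three contrasts (0.0167) | 80.0% | 84.4% |
| Dunnett over two doses | 85.6% | 89.1% |
| Holm | 88.8% | 91.8% |
| Hochberg | 89.4% | 92.3% |
| Pooled contrast first, then each dose, all at 0.05 | 90.1% | 92.8% |
| Fixed order, second dose tested | 84.4% | 88.2% |

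In a fixed order the first dose keeps its unadjusted power. Pooled-first is a closed test of the two dose hypotheses, so it controls the familywise rate. The 90% is therefore computed unadjusted and is lost under single-step adjustment at 30 per arm, but not under every method that controls error.

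**3. False findings with no adjustment and no true effect (30 per arm, simulated).** At least one p-value below 0.05, two-sided: 9.0% over the two doses, 9.6% with the pool added. In the direction of benefit: 4.5% and 4.8%, against 2.5% for a single contrast.

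**4. How often the contrasts disagree.** This is the share of trials in which at least one dose is significant for benefit and the pool is not, at 30 per arm (1,000,000 simulated trials per scenario):

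| True effects of the two doses | Share |
|---|---|
| 3 and 3 | 1.0% |
| 3 and 1.5 | 10.8% |
| 3 and 0 | 43.3% |

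The last row follows from dilution. The pooled effect is (3 + 0)/2 = 1.5, with standard error 3.5 × √(1.5/30) = 0.783, so the noncentrality is 1.5 / 0.783 = 1.92, just below the critical value of about 1.99. A pooled-first rule would accordingly cut the chance of finding a single effective dose from 91% to 47%.

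**5. The wording side by side.** Sections 11.1 and 11.2 do not call the primary contrasts formal or confirmatory. That status can only be inferred from what they leave unsaid. The unrestricted statement in section 11.8 directly follows one limited to secondary and exploratory endpoints and can carry the same limit. Under that reading, section 11.8 says nothing on the primary contrasts beyond the exploratory label in its opening clause. Under the wider reading, they are exploratory outright. Neither reading produces a formal claim.

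**The case for a change.** The strongest case for a change is that silence leaves room for choice. Section 3.3 gives a reason for unequal dose effects, and in the extreme case a dose contrast and the pool would disagree in 43% of trials. The synopsis omits the exploratory proof-of-concept description, and the SAP that should have settled the matter was never finalized. One sentence naming the two sized contrasts as those of interest and the pool as supportive would cost no subjects and no power.

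The gap itself stands: no section states the multiplicity handling or the deciding contrast for the primary endpoint. The consequence is weaker than it looks. The 43% requires the full planned effect in one dose and none in the other. Section 11.2 plans the same effect for each dose, where disagreement is 1%, and the near-maximal platelet inhibition from 20 mg argues against a zero effect at the lower dose. The 4.5% matters only if any one significant dose is declared a success, and no section says so. The suggested ranking mostly restates what is already there: section 11.2 sizes exactly two contrasts, and section 11.1 brings in the pool as an addition.

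**Conclusion.** No change follows. The protocol leaves the status of the primary contrasts unstated, but an analyst who follows it as written reports two unadjusted dose comparisons, each at two-sided 0.05 and powered as claimed (90.4% at 30 per arm), with the pooled comparison alongside. Those estimates, intervals and per-comparison p-values are valid for what they are. No familywise rate is promised, so none is broken, and a single-step adjustment at 30 per arm would cost about 5 to 6 points of power per dose (85.6% or 84.3% against 90.4%) to protect a claim the study does not make.

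The report can reasonably treat the two sized contrasts as those of interest, treat the pool as supportive, and note the 4.5% chance of at least one false finding of benefit over two doses. That is sensible practice and alters no analysis. With enrolment stopped, the point bears mainly on how results are described. The report contents attached to the Note to File list summaries and a listing of the coronary physiology indices and name no contrast.

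This rests on the study being read as exploratory, as section 11.8 says, and on the planning values in section 11.2. The figures at 33 per arm also need both Stage A doses to carry forward with complete IMR data. A formal efficacy claim from one of the contrasts would need a stated rule, but the plan does not set out to make one.

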11.9. Interim Analysis

No formal interim analysis of efficacy is planned.

11.10. Safety Analyses

Adverse events will be listed and summarized by system organ class and preferred term, as well as according to severity and causality/relationship to temanogrel. Treatment-emergent adverse events (TEAEs) will be summarized by stage, cohort, and treatment group. In addition, TEAEs will be pooled across treatment groups (ie, placebo, temanogrel). Similarly, bleeding events will

be summarized by BARC classification by stage, cohort, and treatment group and pooled across treatment groups. Observed values for clinical laboratory tests, vital signs, and safety 12-lead ECGs, will be summarized by stage, cohort, treatment group, and timepoint. Individual data listings of clinical laboratory tests results will be presented for each subject. Observed values and changes from Baseline will be summarized descriptively. Safety 12-lead ECG data (observed values and change from Baseline) will be listed for each subject and timepoint. Observed values will be classified for normal, abnormality that is not clinically significant, and clinically significant abnormality by stage, cohort, treatment group, and timepoint of collection. Results of other safety assessments will be listed and summarized as appropriate.

A detailed description of all safety analyses will be provided in the SAP.

11.10.1. Safety Endpoints

The safety endpoints will be analyzed using the Safety Set. The primary safety endpoint of the study is the assessment of TEAEs. All bleeding-related adverse events will be classified using the BARC criteria.

- Incidence of all TEAEs
- Incidence of TEAEs by severity
- Incidence treatment-related TEAEs
- Incidence of bleeding-related TEAEs classified using BARC criteria
- Incidence of adverse events leading to discontinuation (if any)
- Incidence of SAEs (if any)
- Incidence and severity of laboratory abnormalities, and change from Baseline in laboratory values (to include hematology, serum chemistry, and coagulation)
- Incidence of clinically significant vital sign abnormalities and changes from Baseline
- Incidence of clinically significant ECG abnormalities and changes from Baseline

11.10.2. Adverse Events

Adverse events will be coded using the Medical Dictionary for Regulatory Activities (MedDRA).

For each treatment group, the proportion of subjects with treatment emergent adverse events will be summarized overall, by severity, and by relationship to study treatment. SAEs will also be summarized by treatment group. A treatment emergent adverse event is defined as:

- An adverse event that occurs after initiation of study treatment that was not present at the time of treatment start.
- An adverse event that increases in severity after the initiation of medication, if the event was present at the time of treatment start.

Adverse events occurring before the first dose of study treatment will be summarized separately.

11.10.3. Clinical Laboratory Parameters

Clinical laboratory parameters will be summarized by treatment group at each scheduled assessment timepoint using descriptive statistics.

In the event of abnormal clinical laboratory values, the Investigator will make a judgment whether or not the abnormality is clinically significant. Clinically significant abnormal values should be reported as adverse events as described in Section 10.8.5.2.

11.10.4. Electrocardiograms

The Investigator is responsible for interpretation of ECG data for eligibility purposes and safety monitoring. ECG data will also be read and interpreted by a central ECG lab. Individual ECG values will be listed by timepoint and summarized using descriptive statistics. Parameters to be provided for each ECG are: HR, RR, PR, QRS, QT, QTc, QTcB, and QTcF. Post-Baseline ECGs for each subject will be compared with the Baseline ECG. Any clinically significant change from Baseline may be recorded as an adverse event if deemed appropriate by the Investigator, or Investigator in consultation with the Clinical Lead. Outlier analysis will be performed on all subjects with QTcF values greater than 500 ms or change from Baseline > 60 ms in the absence of Baseline ECG abnormalities that preclude accurate surface ECG assessment of ventricular repolarization (eg, bundle branch block).

ECG monitoring during catheterization procedures will occur per site standard of care and any clinically significant findings will be recorded as adverse events in the eCRF.

11.10.5. Vital Signs

Vital signs measurements will include blood pressure, heart rate, respiratory rate, and temperature. Vital signs values collected at Screening, Check-in, and prior to discharge will be recorded in the eCRF.

Vital signs monitoring during catheterization procedures will be conducted per site standard of care and any clinically significant findings will be recorded as adverse events in the eCRF.

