1.2. Benefit-Risk Considerations

As of the date of this protocol, the safety, tolerability, PK, and PD of temanogrel have been assessed in 5 Phase 1 studies in healthy subjects. Single and repeated doses of oral temanogrel were evaluated in 4 studies, and single IV doses of temanogrel were evaluated in a separate study. In completed clinical studies, doses of temanogrel planned to be used in this study were well-tolerated and there were no associated safety concerns. The most common adverse events in subjects treated with single doses of IV temanogrel were mild pain and redness at the treatment administration site. In healthy volunteers who received single oral doses of temanogrel, the most common side effects were dizziness and headache, and less commonly tiredness, back pain, skin rash, and nausea.

Although the incidence and severity of MVO in the PCI setting with the chosen study population (elective PCI or PCI for NSTEMI/UA) is reduced compared to primary PCI for STEMI, MVO remains a problem in the chosen study population as impaired microcirculation is often observed in this setting as well. In all patients undergoing PCI, temanogrel is expected to exert antiplatelet and anti-vasoconstrictive effects and improve microvascular coronary perfusion.

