9.2. Treatment Period

Potential eligible subjects (per initial Screening criteria) will undergo Check-in assessments to confirm eligibility on Day 1 (day of PCI procedure) per the Schedule of Assessments ([Appendix 1](#)), including confirmation of lesion-related eligibility by diagnostic angiography (unless performed within 60 days prior to Day 1). These assessments will be performed locally and assessed by the Investigator. Upon confirmation that a subject is eligible for study participation, the subject will be randomized.

Following randomization, in cases when diagnostic angiography is not performed at Check-in, lesion and vessel characteristics should be assessed as part of Baseline target vessel angiographic measures assessment. Similarly, in cases when coronary physiology indices have not been assessed at Check-in for confirmation of suitability for PCI per institutional standards, they should be assessed at Baseline. For all subjects, Baseline peripheral blood samples will be collected. The subject will then be administered study treatment intravenously.

Zero (0) to 2 minutes after the completion of the IV administration of randomized study treatment, a Pre-PCI peripheral blood sample will be drawn followed by measurement of the Pre-PCI coronary physiology indices. Once the Pre-PCI coronary physiology indices have been measured, the PCI procedure will begin. Vital signs and ECG changes will be monitored throughout the procedure per site standard of care and any clinically significant findings will be recorded as adverse events in the eCRF but there are no required study-specific assessments during the conduct of the PCI procedure.

Immediately upon completion of the PCI procedure, the following Post-PCI assessments will be performed: Blood sampling from the coronary ostium and from coronary artery distal to the lesion, coronary physiology indices, target vessel angiographic measures, and peripheral blood sampling. Upon completion of all planned assessments and per the site's standard of care, the subject will be transitioned to the step-down unit at the study center. Additional safety assessments and blood draws prior to discharge will occur per the Schedule of Assessments ([Appendix 1](#)). Subjects will be discharged at the Investigator's discretion based upon clinical presentation, but not prior to the collection of all 6-hour Post-PCI assessments.

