10.9. Order of Events and Priority for Timed Assessments

Every effort should be made to perform procedures as closely as possible to the scheduled times indicated in the Schedule of Assessments ([Appendix 1](#)).

On Day 1, the timing of events should first be determined by subject safety requirements and then by the scheduled times and sequential order of events as described in this protocol, giving consideration to appropriate posture conditions, practical restrictions, and the other procedures scheduled to be performed at the same timepoint. The preferred order of events in the Peri-PCI period is as follows:

1. Diagnostic angiography including confirmation of lesion-related eligibility (not required if a diagnostic angiography obtained within 60 days prior to Day 1 confirms lesion characteristics)
2. Randomization
3. Baseline peripheral blood draw
4. Baseline target vessel angiographic measures (not required to be repeated if completed during diagnostic angiography at Check-in; in cases when diagnostic angiography is not performed at Check-in, lesion and vessel characteristics should be assessed as part of Baseline target vessel angiographic measures assessment prior to administration of study treatment)
5. Baseline coronary physiology indices (IMR, CFR, FFR; not required to be repeated if completed at Check-in for confirmation of suitability for PCI per institutional standards)
6. Treatment administration
7. Post-treatment / pre-PCI peripheral blood draw (collected 0-2 minutes after the end of the IV administration of randomized study treatment)
8. Post-treatment / pre-PCI coronary physiology indices (IMR, CFR, FFR)
9. PCI with predilation (if applicable) and stent deployment
10. Post-PCI (within 15 minutes of the completion of the PCI procedure) coronary artery (coronary ostium and coronary artery distal to the lesion) blood sampling

11. Post-PCI (within 15 minutes of the completion of the PCI procedure) coronary physiology indices (IMR, CFR, FFR)
12. Post-PCI (within 15 minutes of the completion of the PCI procedure) target vessel angiographic measures
13. Post-PCI (within 15 minutes of the completion of the PCI procedure) peripheral blood draw

Specific timing of the study activities listed above is not critical (unless specified) as long as activities are completed in the order specified.

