- ^d If subjects are discharged less than 2 hours after the 6-hour Post-PCI assessments have been completed, any assessments scheduled for discharge must be performed, but assessments scheduled at both 6 hours Post-PCI and discharge do not need to be repeated.
- ^e Subjects will be discharged at the Investigator’s discretion based upon clinical presentation, but not prior to the collection of all 6-hour Post-PCI assessments.
- ^f Site staff will work with subjects who withdraw early to obtain as much follow-up data as possible.
- ^g A physical examination is performed per the site’s standard of care at Screening. A symptom-based physical exam is performed prior to discharge.
- ^h Refer to [Table 2](#) for additional information.
- ⁱ ECG monitoring during catheterization procedures is to occur per site standard of care and any clinically significant findings will be recorded as adverse events in the eCRF.
- ^j To be collected after the completion of the PCI procedure and at least 1-hour postdose.
- ^k Blood pressure and heart rate monitoring during catheterization lab procedures will be conducted per site standard of care and any clinically significant findings will be recorded as adverse events in the eCRF.
- ^l Randomization is to occur after confirmation of all inclusion and exclusion criteria on Day 1.
- ^m Peripheral serotonin is assessed from a blood sample obtained by peripheral venipuncture or preferably using an indwelling catheter (central line can be used if available).
- ⁿ Coronary artery serotonin is assessed from blood samples obtained from the coronary ostium and from coronary artery distal to the lesion using an aspiration catheter.
- ^o To be performed as soon as possible after completion of the PCI procedure.
- ^p Coronary physiology indices include IMR, CFR, and FFR. Assessment of Baseline coronary physiology indices can be performed prior to randomization at Check-in for confirmation of suitability for PCI per institutional standards.
- ^q Confirmation of lesion and vessel characteristics is required for eligibility purposes prior to randomization. Diagnostic angiography including confirmation of lesion-related eligibility can be performed prior to randomization at Check-in or within 60 days prior to Day 1. In cases when diagnostic angiography is not performed at Check-in, lesion and vessel characteristics should be assessed as part of Baseline target vessel angiographic measures assessment prior to administration of study treatment.

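### No blood-pressure value from the first hours after the temanogrel bolus enters the eCRF, so the vital-sign endpoint cannot show an acute pressure change that was not reported as an adverse event

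*Combined protocol and SAP*

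**What the plan says.** Protocol section 11.10.5 fixes which vital signs become data: "Vital signs values collected at Screening, Check-in, and prior to discharge will be recorded in the eCRF". Of these, only the reading before discharge follows dosing. Section 9.2 lets the investigator decide on discharge, "but not prior to the collection of all 6-hour Post-PCI assessments", and Appendix 1 gives that visit a window of 6 h ± 2 h.

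In the catheterization laboratory the plan relies on routine care. Appendix 1, footnote k: "Blood pressure and heart rate monitoring during catheterization lab procedures will be conducted per site standard of care". Sections 9.2, 10.8.1 and 11.10.5 say the same, and add that a clinically significant finding is recorded as an adverse event. The blood-pressure row of Appendix 1 has no mark at Baseline, Dosing, Pre-PCI or immediate Post-PCI.

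Two uses are planned for these data. Section 11.10.1 lists as a safety endpoint "Incidence of clinically significant vital sign abnormalities and changes from Baseline". Sections 10.11 and 11.11 name vital-sign data among what the DSMB reviews when it recommends doses.

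**The concern.** Temanogrel is given as an IV bolus and blocks serotonin-mediated vasoconstriction (sections 1.1 and 6.3). If it lowers arterial pressure, the first hour or so after the bolus is a natural place to look, and the dose rationale in section 3.3 relies on drug coverage in that hour. A change-from-Baseline summary built on readings taken hours later cannot show what happened then. A moderate fall that nobody judges clinically significant leaves no trace in the vital-sign analysis.

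The stake lies mainly in later work. Section 3.2 says the study is to inform the design and dose selection of future studies, and that development is aimed mainly at STEMI and high-risk NSTEMI. The NSTEMI/UA patients enrolled here must be haemodynamically stable (section 4.1). An early pressure difference by arm would help decide whether a later study needs a blood-pressure entry limit or a monitoring rule.

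**Working it through.** The plan gives no figure on this point, so there is none to reproduce.

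**1. Time of the first recorded blood pressure.** Lower limit of the visit window: 6 − 2 = 4 h after PCI. Measured from dosing it is later still, by the bolus (at least 5 min), the Pre-PCI physiology and the PCI itself. In the extracted schedule the single post-dose mark falls in the 6 h column, while the text says before discharge; both give at least 4 h. Blood-pressure values planned for the eCRF vital-sign data between the bolus and that point: 0.

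**2. What else is measured in between.**

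| Source | When | Content | Where it goes |
|---|---|---|---|
| Cath-lab monitoring (App. 1, fn k) | During procedures | Blood pressure, heart rate | AE only, if clinically significant |
| Pre-PCI physiology (9.2, 10.4.1) | After the blood draw at 0–2 min after the bolus | Mean aortic pressure under adenosine | Input to FFR and IMRcorr |
| Post-PCI physiology (10.4.1) | Within 15 min of PCI end | Same | Same |
| 12-lead ECG (App. 1, fn j; 11.10.4) | After PCI and at least 1 h after dosing | Heart rate | ECG summaries |
| Vital signs (11.10.5) | At least 4 h after PCI | Blood pressure, heart rate | Vital-sign endpoint |

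So heart rate has an earlier number, and blood pressure does not. The aortic pressure exists as an input to the indices but is not assigned to the vital-sign analysis.

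**3. Parent-drug exposure at the late reading.** From section 3.3, 40 mg IV: mean Cmax 1840 ng/mL and mean AUC0-t 732, read here as ng·h/mL. If concentration does not rise after the 5-minute bolus, C(t) ≤ 732 / (t − 5/60).
- t = 4 h: 732 / 3.917 = 187 ng/mL, and 187 / 1840 = 10.2% of Cmax.
- t = 6 h: 732 / 5.917 = 124 ng/mL, or 6.7%.

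This bounds parent drug only. M1 and M2 are active and their time courses are not given.

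**4. Timing of Pre-PCI readings.** Section 9.2 sets the order: "a Pre-PCI peripheral blood sample will be drawn followed by measurement of the Pre-PCI coronary physiology indices". Section 10.9 leaves clock time open: "Specific timing of the study activities listed above is not critical (unless specified) as long as activities are completed in the order specified". Assuming one-compartment decline, the area during the bolus is 0.5 × 1840 × 5/60 = 76.7, the remainder is 732 − 76.7 = 655.3, and k = 1840 / 655.3 = 2.81 per h. Parent drug is then 79%, 50% and 25% of peak at 5, 15 and 30 min after the bolus, which is why clock times are needed.

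**5. Precision.** The 95% CI half-width for change v placebo is t(0.975, df) × SD × √(1/n1 + 1/n0). Planned pooled numbers, if 20 and 40 mg both go into Stage B: 4 + 29 = 33 per dose and 2 + 2 + 29 = 33 on placebo. The documents give no SD; 5 to 15 mmHg is assumed. Final numbers are not given either, so smaller cases are shown.

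| Subjects | SD 5 | SD 10 | SD 15 |
|---|---|---|---|
| 33 v 33 | ±2.5 | ±4.9 | ±7.4 |
| 20 v 20 | ±3.2 | ±6.4 | ±9.6 |
| 10 v 10 | ±4.7 | ±9.4 | ±14.1 |
| 4 v 2 (one Stage A cohort) | ±12 | ±24 | ±36 |

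**6. Power.** Two-sided t-test at 0.05, 33 v 33, assumed true falls:

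| Fall | SD 10 | SD 15 | SD 20 |
|---|---|---|---|
| 10 mmHg | 98% | 76% | 52% |
| 5 mmHg | 52% | 27% | 17% |

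**7. What AE reporting would catch.** Take a 10 mmHg mean fall, SD 10, normal, 33 v 33. If falls above 30 mmHg are flagged (assumption), 2.28% v 0.135% of subjects qualify, or 0.75 v 0.04 expected, with Fisher power near zero. Above 20 mmHg, 15.9% v 2.28%, or 5.2 v 0.75 expected, with 26% power.

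**The case against.** The plan's position is coherent. Patients are monitored throughout, clinically significant changes become adverse events, and the DSMB reviews adverse events. Section 3.3 reports close monitoring of cardiovascular parameters in Phase 1 at these exposures with no notable adverse effects. Section 1.2 says "The most common adverse events in subjects treated with single doses of IV temanogrel were mild pain and redness at the treatment administration site". The same rule is stated in several places, so it is a deliberate choice, and vital signs are to be summarised descriptively, not tested. All of this stands, and it keeps the point optional.

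A reader might infer more than the documents support:
- **That early heart rate is missing too.** It is not; the post-PCI ECG supplies it.
- **That the late reading is taken after the effect has gone.** This is unknown. Section 3.3 reports "near maximal inhibition at doses of 20 mg and greater over 4 hours after dosing", which concerns platelets and does not say that the effect ended at 4 h. The exposure bound covers parent drug only.
- **That recorded values would detect an effect with 98% power where AE reporting has almost none.** That is a favourable corner. The size of fall, the SD and the flagging thresholds are all assumed, and a 5 mmHg fall at SD 10 has 52% power.
- **That escalation from 20 to 40 mg was left without decisive data.** At 4 v 2, a half-width of ±24 mmHg (SD 10) would not have guided it. The DSMB charter is also not among the documents, so what the board sees is inferred from the protocol.

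The proposed readings are also noisy. Baseline physiology uses an adenosine infusion and, in the preferred order of section 10.9, comes directly before the bolus. Monitor readings can be disturbed by it as well as the hyperaemic aortic pressures. That is a reason to look at the SD 20 column.

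**Conclusion.** The point holds for blood pressure. Followed exactly, the plan collects no post-dose blood pressure for its vital-sign endpoint until at least 4 h after PCI, and earlier changes survive only if judged clinically significant. The timing follows from the text alone. Its importance rests on mechanism, since the documents report no hypotension signal.

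At the planned size, the missing comparison would have had a half-width of about ±4.9 mmHg at SD 10. That is enough to describe a shift of around 10 mmHg and too little to settle one of 5 mmHg. This is a cheap improvement that could be made, and it does not affect the primary endpoint. The Note to File of 07 October 2022 records that development was discontinued and enrolment ended on 25 August 2022, which narrows what can still be done here.

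**What to change.** In section 11.10.5:
1. Enter in the eCRF, with clock time, the monitored blood pressure at three points: before the bolus (before the Baseline adenosine infusion or after its washout), at Pre-PCI before adenosine starts, and at Post-PCI. Include these in the vital-sign change-from-Baseline summaries. Treat Post-PCI values as supportive, because they follow stenting.
2. Add one table and one listing of within-subject change in mean aortic pressure from Baseline to Pre-PCI, both under the 140 µg/kg/min adenosine dose of section 6.7.1. Flag subjects whose Baseline physiology was recorded at Check-in.

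For both, give each dose against placebo with a 95% CI in the pooled data, and list individual values in Stage A.

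Cost: 3 × 99 = 297 entries of values already on the monitor, plus one table and one listing, with no new procedure. Downsides: cath-lab monitoring and Pre-PCI timing are not standardised, adenosine may mask an effect, permitted intra-arterial verapamil adds noise, and Stage A estimates stay imprecise. The aortic-pressure field in the physiology data transfer must be confirmed, since the operation manual is not shown.

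For this trial, step 2 on stored recordings is what remains practical; step 1 would suit a successor study.
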